[figure not shown]

CLINICAL STUDY PROTOCOL

Document Number:		c02362157-07
EudraCT No.:	n/a	
BI Study No.:	352.2069	
BI Investigational Product(s):	n/a	
Title:	Observational study in healthy subjects and patients with COPD to assess the relationship between clinical, imaging and biomarker measurements, and progression of emphysema over three years [FOOTPRINTS®].	
Brief Title:	Emphysema Progression Biomarker Study	
Clinical Phase:	n/a	
Trial Clinical Monitor:	 Phone: +  Fax: + 	
Project Advisor:		
Status:	Final Protocol (Revised Protocol (based on Global Amendment 5))	
Version and Date:	Version: 6.0	Date: 24 Feb 2020
Page 1 of 88		
Proprietary confidential information.		
© 2020 Boehringer Ingelheim International GmbH or one or more of its affiliated companies. All rights reserved.		
This document may not - in full or in part - be passed on, reproduced, published or otherwise used without prior written permission.		

CLINICAL STUDY PROTOCOL SYNOPSIS

Name of company:	Boehringer Ingelheim		
Name of finished product:			
n/a			
Name of active ingredient:			
n/a			
Protocol date: 02 Sep 2015	Study number: 352.2069		Revision date: 24 Feb 2020
Title of study:	Observational study in healthy subjects and patients with COPD to assess the relationship between clinical, imaging and biomarker measurements, and progression of emphysema over three years [FOOTPRINTS®].		
Coordinating Investigator:	n/a		
Study site(s):	Multi-center, multi-national study, ~ 12 participating countries, ~ 50 sites.		
Clinical phase:	n/a		
Objective(s):	The overall objective of this study is to explore, if any of the biomarkers (soluble, functional imaging and physiological) assessed within healthy subjects, patients with COPD and patients with COPD and A1ATdeficiency are correlated to COPD disease progression, particularly emphysema progression over 156 weeks.		
Methodology:	Prospective, longitudinal study.		
No. of subjects:			
total entered:	Up to 455 subjects entered including: 
• 60 Healthy subjects without airflow limitation• 125 patients with COPD GOLD 1• 125 patients with COPD GOLD 2• 125 patients with COPD GOLD 3• Up to 20 patients with COPD and A1AT deficiency (ZZ genotype)		
Diagnosis:	
• Healthy Subjects• COPD GOLD grade 1, 2, 3• COPD and A1AT deficiency (ZZ genotype)		

Proprietary confidential information © 2020 Boehringer Ingelheim International GmbH or one or more of its affiliated companies

Name of company:	Boehringer Ingelheim		
Name of finished product:			
n/a			
Name of active ingredient:			
n/a			
Protocol date: 02 Sep 2015	Study number: 352.2069		Revision date: 24 Feb 2020
Main criteria for inclusion:	
• COPD and healthy subjects of both sex aged ≥ 40 and ≤ 70 years• COPD with A1ATD of both sex aged ≥ 30 and ≤ 70 years• COPD and healthy ex-smokers with a smoking history ≥ 20 pack years• COPD with A1ATD ex-smokers with a smoking history ≥ 10 pack years• Body mass index (BMI) of ≥ 18 and ≤ 35 kg/m^2 (≤ 30 kg/m^2 in the MRI substudy)		
Duration of observation:	156 weeks (~ 3 years)		
Assessments:	
Clinical assessments:
 
• Spirometry• Body plethysmography• Pulse oximetry• Diffusing capacity of the lung for carbon monoxide• Questionnaires: mMRC, CAT, SGRQ• BODE index• 6 minute walk test (6 MWT)• Medical Events of Special Interest (MESI)• Adverse Events 
Biofluids:
 
• Blood• Induced Sputum (at selected sites) 
Imaging assessments:
 
• Chest CT (inspiratory/expiratory)• Magnetic Resonance Imaging (MRI) (in a subset of healthy subjects and patients with COPD without A1ATD)		
Biobanking:	Unspecified biomarker testing in blood in all subjects and sputum in a subset of subjects		
Safety criteria:	Vital signs, physical examination, safety laboratory, urine pregnancy testing, 12-lead electrocardiogram (ECG) and adverse event reporting		
Statistical methods:	Descriptive statistics, Pearson and rank-based correlation, multivariate statistical prediction model		

FLOWCHART

Study Periods	Screening Period	Observational Period									
		1	2	3	4	5	6	7	8	9	10
Visit		1									
Weeks			12	26	39	52	65	78	91	104	
Days	Prior to any study related procedure	-28 to -1	1	84	182	273	364	455	546	637	728
Time window for visits			see ¹⁷	± 7d	± 14d	± 14d	± 14d	± 14d	± 14d	± 14d	± 14d
Informed consent ¹	X										
Demographics	X										
Medical history	X										
Physical examination, BMI ¹⁰	X						X				X
Vital signs	X						X				X
Review of in-/exclusion criteria	X	X ¹²									
MESI Check	X	X	X	X	X	X	X	X	X	X	X
Smoking Status/Cotinine Test ¹⁸	X	X	X	X			X				X
Restrictions Check ⁸	X	X		X			X				X
Urine pregnancy test ²	X	X		X			X				X
Safety laboratory ^{3,5}	X	X	X	X			X				X
A1ATD testing ¹⁴	X										
12 lead-ECG	X						X				X
BODE index ¹⁵		X									X
mMRC ⁴	X	X					X				X
CAT ⁴		X					X				X
SGRQ ⁴		X					X				X
Pulse oximetry	X	X		X			X				X
Spirometry (PFT) ¹⁹	X	X	see ²¹	X			X				X
Lung diffusion capacity ²⁰	X	X		X			X				X
Body plethysmography ²⁰		X		X			X				X
Chest CT		X					X				X
MRI (in a substudy only) ⁷		X		X			X				X
Induced sputum ¹⁶		X	X	X			X				X
6 minute walk test (6 MWT)		X ¹¹	X								X
BM blood collection ⁵		X	X	X			X				X
DNA banking (optional) ⁹		X									
Re-/Dispense and review subject reminder diary ¹³		X	X	X	X	X ²²	X	X ²²	X ²²	X ²²	X
Adverse events		X	X	X	X	X	X	X	X	X	X
Concomitant therapy		X	X	X	X	X	X	X	X	X	X
IRT subject visit registration		X	X	X	X	X	X	X	X	X	X
Completion of subject participation											
Vital status and COPD exacerbation status collection ⁶							X				X

FLOWCHART (continued)

Study Periods	Observational Period			
Visit				7
Weeks	117	130	143	156
Days	819	910	1001	1092
Time window for visits	± 14d	± 14d	± 14d	± 14d
Informed consent ¹				
Demographics				
Medical history				
Physical examination, BMI ¹⁰				X
Vital signs				X
Review of in-/exclusion criteria				
MESI Check	X	X	X	X
Smoking Status/Cotinine Test ¹⁸				X
Restrictions Check ⁸				X
Urine pregnancy test ²				X
Safety laboratory ^{3,5}				X
A1 ATD testing ¹⁴				
12 lead-ECG				X
BODE index ¹⁵				X
mMRC ⁴				X
CAT ⁴				X
SGRQ ⁴				X
Pulse oximetry				X
Spirometry (PFT) ¹⁹				X
Lung diffusion capacity ²⁰				X
Body plethysmography ²⁰				X
Chest CT				X
MRI (in a substudy only) ⁷				X
Induced sputum ¹⁶				X
6 minute walk test (6 MWT)				X
BM blood collection ⁵				X
DNA banking (optional) ⁹				
Re-/Dispense and review subject reminder diary ¹³	X ²²	X ²²	X ²²	X
Adverse events	X	X	X	X
Concomitant therapy	X	X	X	X
IRT subject visit registration	X	X	X	X
Completion of subject participation				X
Vital status and COPD exacerbation status collection ⁶				X

Proprietary confidential information © 2020 Boehringer Ingelheim International GmbH or one or more of its affiliated companies

- 1 All subjects must sign an informed consent consistent with ICH-GCP guidelines prior to participation in the study, which includes the application of medication short-term restrictions prior to lung function testing. Re-consenting may become necessary when new relevant information becomes available and should be conducted according to the sponsor's instructions
- 2 Urine pregnancy testing in women of childbearing potential only (to be assessed prior to blood collection and imaging assessments)
- 3 A full panel of hematology, blood chemistry, and coagulation parameters will be done at visits 1, 2, 5, 6 and 7. The reduced panel comprises hematology, [REDACTED], and creatinine at visits 3 and 4. Refer to [Section 5.9.3](#)
- 4 mMRC, followed by CAT and SGRQ in patients with COPD/COPD and A1AT deficiency only will be self-administered at the beginning of the visit and should precede any discussion with a health professional
- 5 Fasted safety and biomarker blood sampling. Dedicated serum and plasma samples for biobanking will be collected in additional tubes
- 6 Phone Call: for all subjects who prematurely discontinue during observational phase. Please refer to [Section 6.2.2](#)
- 7 Prior to each MRI assessment, subject must meet criteria described in [Section 5.3](#)
- 8 Restrictions must be checked at first at the clinic visit. Please refer to [Section 4.2.2](#) and [6.1.1.1](#)
- 9 Blood draw can be done at Visit 2 or any later visit. Refer to [Section 5.8.4](#)
- 10 BMI will be calculated automatically on the eCRF. Refer to [Appendix 10.4.3](#)
- 11 The 6 MWT at Visit 1 will be performed to train the subjects for the procedure
- 12 Criteria, which apply at visit 2 only, not subsequent visits
- 13 Refer to [Section 3.1.1](#)
- 14 Genetic test on A1AT deficiency performed on all subjects
- 15 Done in patient with COPD/COPD and A1ATD only
- 16 Induced Sputum will be collected in all subjects at selected sites only
- 17 Refer to [Section 6.1](#)
- 18 A positive cotinine test is not exclusionary during screening and observational phase but should be explained and documented by the investigator
- 19 Spirometry will be done pre and post Salbutamol (Albuterol) administration at visits indicated in the [flowchart](#)
- 20 Lung diffusion capacity and bodyplethysmography will be done post Salbutamol (Albuterol) administration only at visits indicated in the flowchart
- 21 FEV₁ measurement to assess safety criteria for the sputum induction procedure can be done on the centrally provided spirometer or on a local device
- 22 At the phone call visits subject reminder diary is reviewed

TABLE OF CONTENTS

TITLE PAGE	1
CLINICAL STUDY PROTOCOL SYNOPSIS.....	2
FLOWCHART	4
TABLE OF CONTENTS	7
ABBREVIATIONS	11
1. INTRODUCTION.....	14
1.1 MEDICAL BACKGROUND	14
2. RATIONALE, OBJECTIVES, AND BENEFIT - RISK ASSESSMENT	16
2.1 RATIONALE FOR PERFORMING THE STUDY	16
2.3 BENEFIT - RISK ASSESSMENT.....	17
3. DESCRIPTION OF DESIGN AND STUDY POPULATION	20

10.5	INSTRUCTIONS FOR ASSESSMENTS	80
10.6	COMPUTATION OF BODE INDEX	80
10.7	GLOMERULAR FILTRATION RATE (GFR)	81
11.	DESCRIPTION OF GLOBAL AMENDMENT(S)	82

ABBREVIATIONS

A1AT	Alpha-1 Antitrypsin
A1PI	Alpha-1 Proteinase Inhibitor
AE	Adverse Event
ANOVA	Analysis of Variance
AP/ALP	Alkaline Phosphatase
aPTT	Activated Partial Thromboplastin Time
ATS	American Thoracic Society
AUC	Area under the curve
BI	Boehringer Ingelheim
b.i.d.	bis in die (twice daily dosing)
BM	Biomarker
BMI	Body Mass Index
BP	Blood Pressure
CAT	COPD Assessment Test Questionnaire
CART	Classification and Regression Tree
CI	Confidence Interval
CK	Creatine Kinase
CML	Local Clinical Monitor
COPD	Chronic Obstructive Pulmonary Disease
CRA	Clinical Research Associate
CT	Computed Tomography
CSP	Clinical Study Protocol
CSR	Clinical Study Report
DNA	Deoxyribonucleic Acid
eCRF	Electronic Case Report Form
ECG	Electrocardiography/Electrocardiogram
ERS	European Respiratory Society
ERV	Expiratory Reserve Volume
EudraCT	European Clinical Trials Database
FEV ₁	Forced Expiratory Volume in 1 st second
FRC	Functional Residual Capacity
GCP	Good Clinical Practice
GGT/γ-GT	Gamma-Glutamyl Transferase
GLI	Global Lung Function Initiative
GOLD	Global Initiative for Chronic Obstructive Lung Disease
Hb	Hemoglobin
Hct	Hematocrit
IC	Inspiratory Capacity
ICH	International Conference on Harmonisation
IEC	Independent Ethics Committee

[REDACTED]	[REDACTED]
i.m.	intramuscular
IRB	Institutional Review Board
IRT	Interactive Response Technology
ISF	Investigator Site File
i.v.	intravenous
IVC	Inspiratory Vital Capacity
JRS	Japanese Respiratory Society
LDH	Lactic Dehydrogenase
MCV	Mean Corpuscular Volume
MCH	Mean Corpuscular Hemoglobin
MCHC	Mean Cellular Hemoglobin Concentration
MedDRA	Medical Dictionary for Drug Regulatory Activities
MESI	Medical Events of Special Interest
mL	Milliliter
MMPs	Matrixmetalloproteinases
mMRC	Modified Medical research Council Dyspnea Scale
MRI	Magnet Resonance Imaging
mSv	milliSievert
µM	Micrometer
NE	Neutrophil Elastase
NSP	Neutrophil-derived Serine Protease
OPU	Operative Unit
PDE-4	Phosphodiesterase 4
PFT	Pulmonary Function Test
p.o.	per os (oral)
PR	Pulse Rate
PRO	Patient Reported Outcome
[REDACTED]	[REDACTED]
q.d.	quaque die (once a day)
RNA	Ribonucleic acid
ROC	Receiver Operating Characteristics
RV	Residual Volume
SAE	Serious Adverse Event
SC	Steering Committee
s.c.	subcutaneous
SGOT	serum glutamic oxaloacetic transaminase
SGPT	serum glutamate-pyruvate transaminase
SGRQ	St George's Respiratory Questionnaire
SOP	Standard Operating Procedure
[REDACTED]	[REDACTED]
Sv	Sievert
TCM	Trial Clinical Monitor
t.i.d.	ter in die (3 times a day)
TMF	Trial Master File
TLC	Total Lung Capacity

TSAP

Trial Statistical Analysis Plan

6 MWT

6 Minute Walk Test

[figure not shown]
1. INTRODUCTION

[figure not shown]
1.1 MEDICAL BACKGROUND

The chronic airflow limitation characteristic of COPD is caused by a mixture of small airways disease (obstructive bronchiolitis) and parenchymal destruction (emphysema), the relative contributions of which vary from patient to patient [[P15-01740](#)]. Estimates for emphysema in patients with COPD vary up to 60%.

There is no treatment for disease progression in COPD, and current treatment options, apart from smoking cessation do not prevent decline of FEV₁ (forced expiratory volume in 1 second) over time, nor inhibit the lung structural damages. COPD is a heterogeneous disease with at least 2 clinical well recognized phenotypes (bronchitic and emphysematous). Both can be present alone or in combination, with varying degrees of severity.

The bronchitis phenotype is defined according to historic clinical criteria, i.e. the presence of cough and sputum on most days over 3 months in 2 consecutive years. Emphysema definition is based on pathological changes identified by radiological/functional outcomes, or ultimately on pathology. Clinical data suggests that the rate of decline of FEV₁ varies across individual patients with COPD regardless of their initial GOLD (Global Initiative for Chronic Obstructive Lung Disease) FEV₁ grade category, with a faster rate of decline observed in the emphysematous phenotype, but also in current smokers, and following COPD exacerbations. The only COPD genotype identified so far is alpha1-antitrypsin deficiency. Severe deficiency of alpha1-antitrypsin is associated with a strong tendency for development of emphysema, often, but not always, panlobular in character and basal in distribution. This emphysema is thought to be the result of inadequate neutralisation of naturally occurring proteases, such as neutrophil elastase, by alpha1 proteinase inhibitor (A1PI), which normally serves as a protease inhibitor [[R15-4639](#)]. It is synthesized predominantly in the liver and functions as a serine proteinase inhibitor or serpin and provides essential protection to lung tissue against the actions of proteolytic enzymes such as neutrophil elastase (NE) and proteinase 3 (PR3). The most common deficient phenotype is PiZ, which encompasses both PiZZ and PiZ null genotypes. The majority of individuals with 'severe pathophysiological deficiency', classified by a serum A1AT level below the putative protective threshold (11 µM), have the PiZZ genotype [[R15-4638](#)].

2. RATIONALE, OBJECTIVES, AND BENEFIT - RISK ASSESSMENT

2.1 RATIONALE FOR PERFORMING THE STUDY

Pharmacological treatment of COPD is currently based on bronchodilators and anti-inflammatory drugs. Approved medicines may relieve symptoms, reduce exacerbations and/or improve health status and exercise tolerance, but there is no treatment for disease progression in COPD, and systematic treatment options, apart from smoking cessation, do not prevent rate of decline of FEV₁ over time, nor inhibit the lung structural damages.

More in depth understanding of COPD patient phenotypes and the course and drivers of COPD disease progression is required to address this unmet medical need and enable drug development aiming at a reduction of COPD disease progression.

Biomarkers may assist, beside clinical parameters, in characterizing patients and potentially in predicting and monitoring their disease course.

[REDACTED]

increase the understanding of the underlying pathophysiology of emphysema progression.

BI plans to conduct this longitudinal emphysema progression biomarker study to identify biomarkers (soluble, functional imaging and physiological) that may be useful in differentiating a patient population with ongoing emphysematous destruction of lung parenchyma, which may enable development of drugs aiming at the reduction of COPD progression.

Rationale for the study extension to 3 years

It has become known from consortia data (████████) that lung density decline, as assessed by CT and lung function decline, do not correlate across GOLD stages [R18-1744]. Therefore, besides characterizing emphysema progression in patients it will be important to also assess lung function decline by spirometry since this describes an additional high risk COPD patient subgroup with a large unmet medical need. Since detection of lung function decline is expected to take longer (3 years) than detection of lung density decline, the study is being extended to a 3 year observation time.

This study will include 60 healthy subjects (ex-smokers without airflow limitation), 125 COPD GOLD 1, 125 COPD GOLD 2, 125 COPD GOLD 3, and up to 20 patients with COPD and A1AT deficiency (ZZ genotype). Soluble and imaging biomarkers will be investigated addressing different aspects of disease pathways postulated to be relevant for COPD

2.2

2.3 BENEFIT - RISK ASSESSMENT

This study is an observational study with no alteration in patient's usual medication treatment. There will be no direct benefit for the participating subjects except the benefit which derives from the periodic monitoring of their health or disease status by the investigator and site staff. All subjects are allowed to continue their usual care. The subject's participation in the study requires standard medical procedures known to patients with respiratory diseases. The examinations include common procedures like

physical examination, cotinine test to determine smoking status, 12-lead ECG, spirometry, body plethysmography, and DLCO. Induction of sputum could result in bronchoconstriction and is performed after bronchodilation, but is usually quickly reversible with short acting β -2-agonist treatment [[R12-5301](#)].

Other procedures include common medical practices such as disease-specific questionnaires, routine blood sampling for safety assessment, and biomarker collection. All these procedures are known to have an acceptable safety risk and may also be performed in healthy volunteers. A total blood volume of approximately 500 mL will be drawn over a period of about 3 years. Approximately 12 mL will be drawn at the screening visit and approximately 80 to 90 mL per biomarker sampling time point (Visit 2 – 7). This is much less than the volume of a normal blood donation (400 mL). No safety-related risk to the patients is expected from this blood withdrawal.

Monitoring for pregnancy will occur at the screening visit and prior to imaging procedures (CT and MRI) at Visits 2, 4, 5, 6, and 7 in order to avoid further risk. Pregnant women will be discontinued from further study participation, but should be followed up for vital status and COPD exacerbation status collection.

Imaging examinations are important components of this study. Chest CT plays a pivotal role to analyze pathologies of pulmonary emphysema not only in its morphological aspect but also in the assessment of severity. CT will also contribute to the phenotyping of COPD, such as primarily parenchymal disease or primarily airway disease [[R15-4823](#)].

The annual exposure from natural background radiation is 2 – 3 mSv. The radiation dose applied per chest CT scan is approximately 5 times lower than the maximum effective annual dose limit of 20 mSv for people occupationally exposed (radiation workers) in Germany and about 12 times lower than the annual dose limit of 50 mSv for radiation workers in the US. The level of exposure of the chest CT scans is associated with a low additional lifetime risk of cancer (0.02 %), based on the assumption of the International Commission on Radiological Protection (ICRP) of 2007 [[R15-3219](#)] estimating an excess life-time cancer mortality risk of about 5% per Sv. Subjects with an increased risk of lung cancer (e.g. ex-smokers and smokers) may benefit from the CT assessment [[R12-3778](#)], considering the sensitivity of chest CT for lung cancer, critical for treatment success.

Chest CT scans will be performed in 40 to 70 years old subjects (30 to 70 years in patients with COPD and A1ATD) to accurately assess lung disease including emphysema, air trapping, small airway disease, and airway wall thickness.

Magnet Resonance Imaging (MRI) will be conducted in a subset of subjects (substudy). MRI uses strong magnetic fields and radio waves to generate cross-sectional images of the body. In this study, MRI will be used to acquire morphological and functional information of the lungs and the heart. In contrast to CT, MRI does not use ionizing radiation (X-rays) and there are no known harmful effects associated with temporary exposure to the strong magnetic field of MRI scanners in patients without foreign bodies. Potential safety concerns are related to implanted medical devices, which can malfunction or heat up during the exams. Dyes from tattoos and tattooed eyeliners can cause skin or eye irritation, and medication patches can cause skin burn due to heating effects. Some subjects might suffer from claustrophobia

Proprietary confidential information © 2020 Boehringer Ingelheim International GmbH or one or more of its affiliated companies

during the examination. Subjects in the MRI scanner will be exposed to some noise, which will be minimized by ear protection but can still cause some discomfort. The use of contrast agent during the examinations is accompanied with a slight risk of an allergic reaction. However, the risk of a significant allergic reaction is 1:150,000 examinations. Additionally, MRI contrast agents can cause problems in patients with significant kidney disease. To minimize the risk, kidney function will be measured before the MRI scans. Only male and non-pregnant female subjects (without implanted devices susceptible to magnetic influence) who present with stable clinical conditions and tolerate repeated MRI scanning will be considered for inclusion into the study.

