5.2 COMPUTED TOMOGRAPHY (CT)

A chest CT scan will be performed as indicated in the [flowchart](#) according to specifications detailed in the Central Imaging Vendor manual. A low dose inspiratory chest CT scan [REDACTED] to assess airway wall thickness and emphysema and an expiratory scan [REDACTED] to assess air trapping will be performed. To achieve optimal image quality, the chest CT will be done with subjects being in a state of bronchodilation, e.g. after administration of salbutamol (albuterol). Before beginning the chest CT scan, the inspiration/expiration maneuvers should be explained carefully to the subject. All scans on each subject will be completed on the same scanner used for the baseline CT and accredited for use by the Central Imaging Vendor. Chest CT scan will be performed at timepoints given in the flowchart. If a chest CT scan cannot be scheduled during the regular study visit, it has to be performed within 14 days after the visit. In this case, administration of salbutamol (albuterol) should be performed prior to the imaging assessment in patients with COPD as well as in healthy subjects (see [Section 6.1.1.3](#)).

All scans will be digitally transferred for central review within a pre-specified time period. Phantom scans using the COPDGene Phantom have to be carried out regularly for quality

assurance purposes according to the Central Imaging Vendor manual. Further information on chest CT is provided in a separate manual filed in the ISF.

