Interval	Label	Visit	planned	Window	Analysis
			day [days]		Window
					[days]
Observational period	Baseline	2	1	1	≤ 28
Observational period	Week 12	3	84	77 to \leq 91	29 to ≤ 130
Observational period	Week 26	4	182	$168 \text{ to} \leq 196$	131 to \leq 273
Observational period	Week 52	5	364	$350 \text{ to} \leq 378$	274 to \leq 546
Observational period	Week 104	6	728	714 to \leq 742	$547 \text{ to } \leq 910$
Observational period	Week 156	7	1092	1078 to \leq	≥ 911
				1106	

Table 6.7: 6 Time windows for imaging biomarker assessment – CT

Interval	Label	Visit	planned day	Window [days]	Analysis Window
			·		[days]
Observational period	Baseline	2	1	1	≤ 28
Observational period	Week 52	5	364	$350 \text{ to} \leq 378$	29 to \leq 546
Observational period	Week 104	6	728	714 to \leq 742	$547 \text{ to } \leq 910$
Observational period	Week 156	7	1092	1078 to \leq	≥ 911
				1106	

Table 6.7: 7 Time windows for imaging biomarker assessment – MRI

Interval	Label	Visit	planned	Window [days]	Analysis
			day		Window
					[days]
Observational period	Baseline	2	1	1	≤ 28
Observational period	Week 26	4	182	$168 \text{ to } \leq 196$	29 to \leq 273
Observational period	Week 52	5	364	$350 \text{ to } \leq 378$	$274 \text{ to } \leq 546$
Observational period	Week 104	6	728	714 to \leq 742	$547 \text{ to } \leq 910$
Observational period	Week 156	7	1092	$1078 \text{ to } \leq 1106$	≥ 911

Table 6.7: 8 Time windows for symptom questionnaire – mMRC, CAT, SGRQ-COPD

Interval	Label	Visit	planned	Window	Analysis
			day	[days]	Window
					[days]
Observational period	Baseline	2^{1}	1	1	≤ 28
Observational period	Week 52	5	364	$350 \text{ to} \leq 378$	29 to \leq 546
Observational period	Week 104	6	728	714 to \leq 742	$547 \text{ to } \leq 910$
Observational period	Week 156	7 1092 1		1078 to \leq	≥ 911
				1106	

¹ Visit 1 for mMRC (Screening)

Table 6.7: 9 Time windows for safety assessment – physical examination, vital signs

Interval	Label	Visit	planned day	Window [days]	Analysis Window
Screening	Baseline	1	-28 to -	1	[days] < 28
Sercening	Dascinic	1	1	1	
Observational period	Week 52	5	364	$350 \text{ to} \leq 378$	29 to \leq 546
Observational period	Week 104	6	728	714 to \leq 742	$547 \text{ to } \leq 910$
Observational period	Week 156	7	1092	$1078 \text{ to } \leq 1106$	≥ 911

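### Protocol Section 2.3 gives 0.02% as the lifetime cancer risk of the chest CT scans, but this is the risk of one scan; the full four-visit schedule gives about 0.08%

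*Protocol*

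**What the plan says.** Protocol Section 2.3 first describes the dose of one scan: "The radiation dose applied per chest CT scan is approximately 5 times lower than the maximum effective annual dose limit of 20 mSv" that applies to occupationally exposed people in Germany, and "about 12 times lower than the annual dose limit of 50 mSv for radiation workers in the US". The next sentence turns to risk and says that the exposure from the chest CT scans, in the plural, is "associated with a low additional lifetime risk of cancer (0.02" %). It bases this on an international recommendation "estimating an excess life-time cancer mortality risk of about 5% per Sv".

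The Chest CT row of the protocol flowchart is marked at Visit 2 and at weeks 52, 104 and 156. The SAP has the same four time points in Table 6.7: 6, "Time windows for imaging biomarker assessment – CT". Protocol Section 5.2 describes two acquisitions at each time point: "A low dose inspiratory chest CT scan" and an expiratory scan. The details after each are blacked out.

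The visible text of Section 2.3 contains no total radiation dose and no total risk for the three-year schedule. For blood, the same section gives both the amount per sampling time point (about 80 to 90 mL) and the total (about 500 mL over about 3 years).

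**The concern.** The dose sentence is explicitly about one scan. The risk sentence moves to the plural and drops that qualifier, so a reader would naturally take 0.02% as the risk from the CT scans of this study. If the number belongs to one scan, the risk of following the whole schedule is understated by the number of scans.

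This matters because it is a safety figure in the benefit-risk assessment of an observational study. That section says subjects gain no direct benefit beyond the monitoring of their health, although it adds that people at raised risk of lung cancer may gain from CT. Healthy ex-smokers are scanned on the same schedule as patients. What an ethics committee needs to weigh is the exposure from taking part in the study, and under a coefficient expressed per Sv that exposure adds up over scans.

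**Working it through.** **Inputs**

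- Dose of one scan, German comparison (Protocol 2.3): 20 mSv / 5 = 4.0 mSv.
- Dose of one scan, US comparison (Protocol 2.3): 50 mSv / 12 = 4.17 mSv.
- Risk coefficient (Protocol 2.3): 5% per Sv.
- Scheduled CT time points (flowchart; SAP Table 6.7: 6): 4, at Visits 2, 5, 6 and 7.

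**Formula:** risk = number of scans × dose per scan in Sv × 5% per Sv.

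**Reproducing the printed figure.** One scan gives 0.0040 Sv × 5% = 0.020%, or 0.00417 Sv × 5% = 0.021%. Both round to the stated 0.02%.

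**Other numbers of scans**

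| Scans | Total dose (mSv) | Risk | Multiple of 0.02% |
|---|---|---|---|
| 1 | 4.0 to 4.2 | 0.020% to 0.021% | 1.0 |
| 2 | 8.0 to 8.3 | 0.040% to 0.042% | 2.0 to 2.1 |
| 3 (stops after week 104) | 12.0 to 12.5 | 0.060% to 0.063% | 3.0 to 3.1 |
| 4 (reaches Visit 7) | 16.0 to 16.7 | 0.080% to 0.083% | 4.0 to 4.2 |

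Only one scan reproduces 0.02%.

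**Working backwards.** A total risk of 0.02% corresponds to 0.0002 / 0.05 = 0.004 Sv, or 4 mSv (3 to 5 mSv if 0.02% is rounded from 0.015% to 0.025%). Spread over four time points, that is about 1 mSv each, which does not agree with the 4 mSv per scan stated one sentence earlier.

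**Two acquisitions at each time point.** The table takes 4 mSv to cover the inspiratory and expiratory pair. If it covered only one acquisition, and if both had the same dose (an assumption, since the details are blacked out), eight acquisitions would give 8 × 4.0 = 32 mSv and 0.16% (8 × 4.17 = 33.3 mSv and 0.167%). A lower expiratory dose would put the total between the four-scan row and this value.

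**The case against.** The strongest reply is that nothing has been miscalculated. The product of 4 mSv and 5% per Sv is correct, the preceding sentence is about one scan, and the plural may be generic: later in the same section the plural is used simply to say who will be scanned. The sentence does not claim to be a total. The dose, the coefficient and the schedule are all disclosed, so a reader can multiply. The absolute risk remains small and no endpoint, sample size or analysis depends on it.

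Much of this stands. The per-scan reading is possible and the multiplication is right. But the sentence does not say that it is per scan, and even on that reading the section gives no figure for the schedule as a whole, although it does so for blood.

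Three stronger readings are tempting, and the documents do not support them:

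- A reader might infer that the stated risk is at least four times too low. Four is the factor for the full schedule, not a minimum. SAP Section 7 provides for subjects who completed week 104 and did not consent to the third year; they have three scheduled scans. Earlier discontinuation can mean fewer. The plural is also ambiguous, so the shortfall is certain only if 0.02% is read as the study total.
- A reader might infer that the true figure is 0.16%. That needs the 4 mSv to be per acquisition and the two doses to be equal. The relevant text is blacked out, and the synopsis lists the inspiratory and expiratory CT as one assessment, which favours 4 mSv covering the pair.
- A reader might infer that participants were given the lower figure. The consent pages are not in the reviewed documents, so what the subject information says about radiation is unknown.

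**Conclusion.** The point holds as a correction to a stated safety figure. On the protocol's own inputs, 0.02% is the risk of a single scan. The scheduled exposure for a subject who reaches Visit 7 is about 16 to 17 mSv, or about 0.08%, roughly four times the printed number; for a subject who stops after the week 104 scan it is about 0.06%, roughly three times.

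These figures assume that one scan of about 4 mSv covers both acquisitions at a time point and that risk adds linearly with dose, as the quoted coefficient implies. All inputs are approximate, so the factors are too.

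The consequence is limited to the benefit-risk statement. A risk of about 0.08% is still low, and the documents give no ground for saying that the overall benefit-risk conclusion would change. One separate wording point does not affect the factor: the coefficient is for cancer mortality, while the sentence speaks of the risk of cancer.

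**What to change.** In Protocol Section 2.3:

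1. Label 0.02% as the risk of one scan.
2. Add the cumulative figures for the full four-visit schedule: about 16 mSv and about 0.08%.
3. State whether the 4 mSv covers both the inspiratory and the expiratory acquisition. If it does not, recompute the total from the actual doses of the two acquisitions, without assuming that they are equal.
4. Check that the subject information agrees with the corrected text.

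The cost is a sentence or two in the protocol, with a matching edit to the subject information if it differs. The stated figure becomes less favourable. No data collection or analysis changes.
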